#### **10.8.8.2.2. Vaccine-Induced Immunogenicity**

Blood samples will be obtained for immunogenicity testing at the central laboratory.

The SARS-CoV-2 neutralization assay will be run on serum samples obtained for the following strain:

- Omicron XBB.1.5

At designated sites, optional whole blood samples of ~130 mL will be obtained from up to approximately 30 participants ( $\geq 18$  years of age only) for evaluation of boostability and protection against the variant strain for isolation of PBMCs. These samples will be used to describe B-cell and T-cell responses to the variant and the original strains. A blood sample of ~5 mL for HLA typing will also be obtained (at Visit B1 only). Refer to the [SoA](#) for time points of collection.

#### **10.8.8.2.3. N-Binding Antibody Test**

The N-binding antibody test will be performed by the central laboratory at certain blood sample collections to establish prior exposure to SARS-CoV-2 up to the time point. These data will be used for study analyses.

#### **10.8.8.2.4. Biological Samples**

Refer to [Section 8.2.4](#) for general information regarding use and storage of biological samples.

The total blood sampling volume for individual participants at scheduled visits in this study is approximately 50 mL for participants 12 through 17 years of age and approximately 160 mL for participants  $\geq 18$  years of age. Those participants  $\geq 18$  years of age who consent to additional blood collection for isolation of PBMCs and additional serology will have a total blood sampling volume of up to approximately 815 mL. Additional blood samples may be taken for safety assessments at times specified by Pfizer, provided the total volume taken during the study does not exceed 550 mL during any period of 56 consecutive days for participants 18 years of age and older.

Blood sample collection may be halted or discontinued upon notification by Pfizer. This includes discontinuing sampling in dosed participants who are no longer eligible for the study as well as discontinuation for groups of participants or all participants.

### **10.8.8.3. Safety Assessments**

Planned time points for all safety assessments are provided in the [SoA](#). Unscheduled safety measurements may be obtained at any time during the study to assess any perceived safety issues.

#### **10.8.8.3.1. Physical Examinations**

Perform a clinical assessment. If the clinical assessment indicates that a physical examination is necessary to comprehensively evaluate the participant, a physical examination will be performed.

A complete physical examination will include evaluating any clinically significant abnormalities within the following body systems: general appearance; skin; head, eyes, ears, nose, and throat; heart; lungs; abdomen; musculoskeletal; extremities; neurological; and lymph nodes.

Investigators should pay special attention to clinical signs related to previous serious illnesses.

Physical examination findings collected during the study will be considered source data and will not be required to be reported, unless otherwise noted. Any untoward physical examination findings that are identified during the active collection period and meet the definition of an AE or SAE ([Appendix 3](#)) must be reported according to the processes in Sections [8.4.1](#) to [8.4.3](#).

#### **10.8.8.3.2. Vital Signs**

The participant's body temperature will be measured prior to study vaccination.

Any untoward vital sign findings that are identified during the active collection period and meet the definition of an AE or SAE ([Appendix 3](#)) must be reported according to the processes in Sections [8.4.1](#) to [8.4.3](#).

#### **10.8.8.3.3. Clinical Safety Laboratory Assessments**

Clinical safety laboratory assessments will not be collected in this study.

#### **10.8.8.3.4. Electronic Diary**

E-diary assessments are included in Substudy B for participants' reporting of local reactions, systemic events, and antipyretic medication usage for 7 days from the day of administration of the study intervention. Participants will receive reminders to complete the vaccination e-diary on a daily basis, starting on the day of vaccination (Day 1) through Day 7. Refer to [Section 8.3.4](#) for details.

The e-diary is also used as a tool for participants to alert study sites of a COVID-19 diagnosis or symptoms that could represent a potential COVID-19 illness; it is not reported data. Participants will receive reminders to complete the COVID-19 illness e-diary on a weekly basis throughout the study and whenever they receive a diagnosis of COVID-19 or experience symptoms of COVID-19. Refer to [Section 10.8.8.5.7](#) for details.

#### **10.8.8.4. Adverse Events, Serious Adverse Events, and Other Safety Reporting**

Refer to [Section 8.4](#) and the following subsections:

- [Section 8.4.1](#) Time Period and Frequency for Collecting AE and SAE Information
- [Section 8.4.2](#) Methods of Detecting AEs and SAEs
- [Section 8.4.3](#) Follow-Up of AEs and SAEs
- [Section 8.4.4](#) Regulatory Reporting Requirements for SAEs
- [Section 8.4.5](#) Environmental Exposure, Exposure During Pregnancy or Breastfeeding, and Occupational Exposure
- [Section 8.4.6](#) Cardiovascular and Death Events
- [Section 8.4.7](#) Disease-Related Events and/or Disease-Related Outcomes Not Qualifying as AEs or SAEs
- [Section 8.4.9](#) Medical Device Deficiencies
- [Section 8.4.10](#) Vaccination Errors

##### **10.8.8.4.1. Adverse Events of Special Interest**

The following events, if reported, have additional procedures associated with their evaluation; they are, therefore, considered protocol-specified AESIs:

- Confirmed diagnosis of myocarditis or pericarditis occurring within 6 weeks after vaccination. See [Section 10.8.8.5.10](#).
- Potential menstrual cycle disturbances. See [Section 10.8.8.5.11](#).

AESIs are examined as part of routine safety data review procedures throughout the clinical trial and as part of signal detection processes. Should an aggregate analysis indicate that these prespecified events occur more frequently than expected, eg, based on epidemiological data, literature, or other data, then this will be submitted and reported in accordance with Pfizer's safety reporting requirements. Aggregate analyses of safety data will be performed on a regular basis per internal SOPs.

All AESIs must be reported as an AE or SAE, as appropriate, following the procedures described in Sections 8.4.1 through 8.4.4. An AESI is to be recorded as an AE or SAE on the CRF. In addition, an AESI that is also an SAE must be reported using the Vaccine SAE Report Form.

#### **10.8.8.4.1.1. Lack of Efficacy**

The investigator must report signs, symptoms, and/or clinical sequelae resulting from lack of efficacy. Lack of efficacy or failure of expected pharmacological action is reportable to Pfizer Safety **only if associated with an SAE**.

#### **10.8.8.4.2. Genetics**

Refer to [Section 8.6](#).

#### **10.8.8.5. Substudy B Procedures**

##### **10.8.8.5.1. Visit B1 – Study Intervention Administration – Day 1**

Before enrollment and before any study-related procedures are performed, voluntary, written, study-specific informed consent will be obtained from the participant or his/her parent(s)/legal guardian as appropriate. Each signature on the ICD must be personally dated by the signatory. The investigator or his or her designee will also sign the ICD. A copy of the signed and dated ICD must be given to the participant or his/her parent(s)/legal guardian as appropriate. The source data must reflect that the informed consent was obtained before participation in the study.

It is anticipated that the procedures below will be conducted in a stepwise manner. Ensure that procedures listed prior to administration of the vaccine are conducted prior to vaccination and on the day of the vaccination.

- Assign a participant number using the IRT system.
- Obtain the participant's demography (including age in years, sex, race, and ethnicity).
- Obtain medical history, including confirmed COVID-19 diagnosis or asymptomatic positive SARS-CoV-2 test result (NAAT or antigen test), and any other medical history of clinical significance.
- Perform a urine pregnancy test on WOCBP as described in [Section 8.3.6](#).
- Discuss contraceptive use as described in [Section 5.3.1](#).
- Measure the participant's height and weight.

- Perform a clinical assessment. If the clinical assessment indicates that a physical examination is necessary to comprehensively evaluate the participant, perform a physical examination (refer to [Section 10.8.8.3.1](#)), and record any findings in the source documents and, if clinically significant, record any findings on the medical history CRF.
- Record nonstudy vaccinations as described in [Section 10.8.6.9](#).
- Ensure and document that all of the inclusion criteria and none of the exclusion criteria are met.
- On the day of and before vaccination, measure the participant's body temperature.
- Ensure that the participant meets none of the temporary delay criteria as described in [Section 10.8.5.5](#).
- On the day of and before vaccination, obtain a nasal (midturbinate) swab (collected by site staff).
- On the day of and before vaccination, collect a blood sample (approximately 10 mL for participants 12 through 17 years of age and approximately 50 mL for participants  $\geq 18$  years of age) for testing of immunogenicity and N-binding antibody.
- If the participant is part of the group for description of cell-mediated immune responses (select sites only;  $\geq 18$  years of age only; additional consent required),
  - collect a blood sample (approximately 130 mL) for PBMC isolation.
  - collect a blood sample (approximately 5 mL) for HLA typing.
- Site staff will obtain the participant's randomization number using the IRT system and will receive the randomization confirmation report.
- Site staff member(s) assigned to the "unblinded" role, per the delegation log, will obtain the vaccine vial allocation using the IRT. The vaccination visit confirmation report with the study intervention allocation will only be sent to the "unblinded" site staff role.
- Site staff member assigned to the "unblinded" role per the delegation log will dispense/administer 1 dose of study intervention into the deltoid muscle, preferably of the nondominant arm. Please refer to the IPM for further instruction on this process.
- Site staff must observe the participant for at least 30 minutes after study intervention administration for any acute reactions. Record any acute reactions (including time of onset) in the participant's source documents and on the AE page of the CRF, and on an SAE form, as applicable.
- Record AEs as described in [Section 8.4](#).

- Explain the e-diary technologies available for this study (see [Section 8.3.4](#)) and assist the participant or his/her parent(s)/legal guardian in downloading the study application onto the participant's own device or issue a provisioned device if required.
- Provide instructions on e-diary completion and ask the participant or his/her parent(s)/legal guardian to complete the reactogenicity e-diary from Day 1 through Day 7, with Day 1 being the day of vaccination (see [Section 8.3.4.1](#) through [Section 8.3.4.5](#)).
- Provide a measuring device to measure local reactions at the injection site and a thermometer for recording daily temperatures and provide instructions on their use.
- Ask the participant or his/her parent(s)/legal guardian to contact the site staff or investigator immediately if the participant experiences any of the following from Day 1 through Day 7 after vaccination (where Day 1 is the day of vaccination) to determine if an unscheduled reactogenicity visit is required:
  - Fever  $\geq 39.0^{\circ}\text{C}$  ( $\geq 102.1^{\circ}\text{F}$ ).
  - Redness or swelling at the injection site measuring greater than 10 cm ( $>20$  measuring device units).
  - Severe pain at the injection site.
  - Any severe systemic event.
- Ask the participant or his/her parent(s)/legal guardian to contact the site staff or investigator if a medically attended event (eg, doctor's visit, emergency room visit) or hospitalization occurs.
- Provide instructions on COVID-19 illness e-diary completion and ask the participant or his/her parent(s)/legal guardian to complete the COVID-19 illness e-diary if the participant is diagnosed with COVID-19 or has possible new or increased symptoms, and when he/she receives a reminder, at least weekly. See [Section 10.8.8.5.7](#) for further details. Provide instructions for use of the provided thermometer to monitor for fever (for COVID-19 surveillance).
- Provide a self-swab kit in case of COVID-19 symptoms and provide instructions on self-collection of nasal swabs.
- Ask the participant or his/her parent(s)/legal guardian to contact the site staff or investigator immediately if the participant experiences acute chest pain, shortness of breath, or palpitations (see [Section 10.8.8.5.10](#)).
- Schedule an appointment for the participant to return for the next study visit.

- Remind the participant or his/her parent(s)/legal guardian to bring the e-diary device to the next visit.
- Complete the source documents.
- The investigator or an authorized designee completes the CRFs and a dispenser/administrator updates the study intervention accountability records.
- The investigator or appropriately qualified designee reviews the reactogenicity e-diary data online following vaccination to evaluate participant compliance and as part of the ongoing safety review. Daily review is optimal during the active diary period.

#### **10.8.8.5.2. Visit B2 – 1-Week Follow-Up Visit (6 to 8 Days After Visit B1)**

- Perform a clinical assessment. If the clinical assessment indicates that a physical examination is necessary to comprehensively evaluate the participant, perform a physical examination, per [Section 8.3.1](#), and record any findings in the source documents and, if clinically significant, record any findings on the AE CRF.
- Record nonstudy vaccinations as described in [Section 10.8.6.9](#).
- Record details of any of the prohibited medications specified in [Section 10.8.6.9.1](#) received by the participant if required for his or her clinical care.
- Record AEs as described in [Section 8.4](#).
- Discuss contraceptive use as described in [Section 5.3.1](#).
- Collect a blood sample (approximately 10 mL for participants 12 through 17 years of age at the time of consent, and approximately 20 mL for participants  $\geq 18$  years of age) for immunogenicity testing.
- If the participant is part of the group for description of cell-mediated immune responses (select sites only;  $\geq 18$  years of age only; additional consent required), collect a blood sample (approximately 130 mL) for PBMC isolation.
- Review the participant's reactogenicity e-diary data. Collect stop dates of any reactogenicity e-diary events ongoing on the last day the reactogenicity e-diary was completed.
- If the 7-day reactogenicity period is ongoing: Remind the participant or his/her parent(s)/legal guardian to contact the site staff or investigator immediately if the participant experiences any of the following from Day 1 through Day 7 after vaccination (where Day 1 is the day of vaccination) to determine if an unscheduled reactogenicity visit is required:

- Fever  $\geq 39.0^{\circ}\text{C}$  ( $\geq 102.1^{\circ}\text{F}$ ).
  - Redness or swelling at the injection site measuring greater than 10 cm ( $>20$  measuring device units).
  - Severe pain at the injection site.
  - Any severe systemic event.
- Remind the participant or his/her parent(s)/legal guardian to contact the site staff or investigator if a medically attended event (eg, doctor's visit, emergency room visit) or hospitalization occurs.
  - Ask the participant or his/her parent(s)/legal guardian to contact the site staff or investigator immediately if the participant experiences acute chest pain, shortness of breath, or palpitations (see [Section 10.8.8.5.10](#)).
  - Ask the participant or his/her parent(s)/legal guardian to contact the site staff or investigator (this could be via the COVID-19 illness e-diary) immediately if the participant experiences any symptoms as detailed in [Section 10.8.8.5.7](#).
  - Ensure that the participant has a self-swab kit in case of COVID-19 symptoms and provide instructions on self-collection of nasal swabs.
  - Schedule an appointment for the participant to return for the next study visit.

#### **10.8.8.5.3. Visit B3 – 1-Month Follow-Up Visit (28-35 Days After Visit B1)**

- Perform a clinical assessment. If the clinical assessment indicates that a physical examination is necessary to comprehensively evaluate the participant, perform a physical examination, per [Section 8.3.1](#), and record any findings in the source documents and, if clinically significant, record any findings on the AE CRF.
- Record nonstudy vaccinations as described in [Section 10.8.6.9](#).
- Record details of any of the prohibited medications specified in [Section 10.8.6.9.1](#) received by the participant if required for his or her clinical care.
- Record AEs as described in [Section 8.4](#).
- Confirm contraceptive use as described in [Section 5.3.1](#).
- Collect a blood sample (approximately 10 mL for participants 12 through 17 years of age at the time of consent, and approximately 50 mL for participants  $\geq 18$  years of age) for immunogenicity testing.

- If the participant is part of the group for description of cell-mediated immune response (select sites only;  $\geq 18$  years of age only; additional consent required), collect a blood sample (approximately 130 mL) for PBMC isolation.
- Review the participant's reactogenicity e-diary data. Collect stop dates of any reactogenicity e-diary events ongoing on the last day the reactogenicity e-diary was completed and record stop dates in the CRF, if required.
- Remind the participant or his/her parent(s)/legal guardian to contact the site staff or investigator if a medically attended event (eg, doctor's visit, emergency room visit) or hospitalization occurs.
- Ask the participant or his/her parent(s)/legal guardian to contact the site staff or investigator immediately if the participant experiences acute chest pain, shortness of breath, or palpitations (see [Section 10.8.8.5.10](#)).
- Ask the participant or his/her parent(s)/legal guardian to contact the site staff or investigator (this could be via the COVID-19 illness e-diary) immediately if the participant experiences any symptoms as detailed in [Section 10.8.8.5.7](#).
- Ensure that the participant has a self-swab kit in case of COVID-19 symptoms and provide instructions on self-collection of nasal swabs.
- Schedule an appointment for the participant to return for the next study visit.
- Complete the source documents.
- The investigator or an authorized designee completes the CRFs.

#### **10.8.8.5.4. Visit B4 – 3-Month Follow-Up Visit (84-98 Days After Visit B1)**

- Record nonstudy vaccinations as described in [Section 10.8.6.9](#).
- Record details of any of the prohibited medications specified in [Section 10.8.6.9.1](#) received by the participant if required for his or her clinical care.
- Record AEs as described in [Section 8.4](#).
- Collect a blood sample (approximately 10 mL for participants 12 through 17 years of age at the time of consent, and approximately 20 mL for participants  $\geq 18$  years of age) for immunogenicity testing, unless advised otherwise by Pfizer.
- If the participant is part of the group for description of cell-mediated immune response (select sites only;  $\geq 18$  years of age only; additional consent required), collect a blood sample (approximately 130 mL) for PBMC isolation.

- Remind the participant or his/her parent(s)/legal guardian to contact the site staff or investigator if a medically attended event (eg, doctor's visit, emergency room visit) or hospitalization occurs.
- Ask the participant or his/her parent(s)/legal guardian to contact the site staff or investigator (this could be via the COVID-19 illness e-diary) immediately if the participant experiences any symptoms as detailed in [Section 10.8.8.5.7](#).
- Ensure that the participant has a self-swab kit in case of COVID-19 symptoms and provide instructions on self-collection of nasal swabs.
- Schedule an appointment for the participant to return for the next study visit.
- Complete the source documents.
- The investigator or an authorized designee completes the CRFs.

#### **10.8.8.5.5. Visit B5 – 6-Month Follow-Up Visit (175-189 Days After Visit B1)**

- Record nonstudy vaccinations as described in [Section 10.8.6.9](#).
- Record details of any of the prohibited medications specified in [Section 10.8.6.9.1](#) received by the participant if required for his or her clinical care.
- Record AEs as described in [Section 8.4](#).
- Collect a blood sample (approximately 10 mL for participants 12 through 17 years of age at the time of consent, and approximately 50 mL for participants  $\geq 18$  years of age) for immunogenicity testing, unless advised otherwise by Pfizer.
- If the participant is part of the group for description of cell-mediated immune response (select sites only;  $\geq 18$  years of age only; additional consent required), collect a blood sample (approximately 130 mL) for PBMC isolation.
- Collect the participant's e-diary provisioned device or assist the participant or his/her parent(s)/legal guardian to remove the study application from his or her own personal device.
- Complete the source documents.
- The investigator or an authorized designee completes the CRFs.

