#### **10.7.8.5.5. Visit A5 – 6-Month Follow-Up Visit (175-189 Days After Visit A1)**

- Record nonstudy vaccinations as described in [Section 10.7.6.9](#).
- Record details of any of the prohibited medications specified in [Section 10.7.6.9.1](#) received by the participant if required for his or her clinical care.
- Record AEs as described in [Section 8.4](#).
- Collect a blood sample (approximately 10 mL for participants 12 through 17 years of age at the time of consent, and approximately 20 mL for participants  $\geq 18$  years of age) for immunogenicity testing, unless advised otherwise by Pfizer.
- If the participant is part of the group for description of cell-mediated immune response (select sites only;  $\geq 18$  years of age only; additional consent required), collect a blood sample (approximately 130 mL) for PBMC isolation.
- Collect the participant's e-diary provisioned device or assist the participant or his/her parent(s)/legal guardian to remove the study application from his or her own personal device.

- Complete the source documents.
- The investigator or an authorized designee completes the CRFs.

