Visit Window	Day 1	6 to 8 Days After Visit B1	28 to 35 Days After Visit B1	84 to 98 Days After Visit B1	175 to 189 Days After Visit B1	Optimally Within 3 Days After Potential COVID-19 Illness Onset	Visit B4 and Visit B5 may be performed as telehealth visits if the participant had blood draws discontinued.
Record nonstudy vaccine information	X	X	X	X	X	X	Refer to Section 10.8.6.9 .
Record prohibited medication use		X	X	X	X	X	Refer to Section 10.8.6.9.1 .
Confirm eligibility	X						Refer to Section 10.8.5.1 and Section 10.8.5.2 .
Measure body temperature	X						
Review temporary delay criteria	X						See Section 10.8.5.5 .
Nasal (midturbinate) swab for SARS-CoV-2 NAAT	X					X	
Blood sample for immunogenicity assessments	~50 mL/ 10 mL	~20 mL/ 10 mL	~50 mL/ 10 mL	~20 mL/ 10 mL	~20 mL/ 10 mL		50 mL/20 mL is to be collected from participants ≥18 years of age at time of consent; 10 mL is to be collected from participants 12 through 17 years of age at time of consent.  Blood sample collection may be halted or discontinued upon notification by Pfizer.
Blood sample for PBMC isolation	~130 mL	~130 mL	~130 mL	~130 mL	~130 mL		Applicable at designated sites, only. Optional with additional consent given by participants ≥18 years of age. See Section 10.8.8.2.2 .

Visit Identifier	B1	B2	B3	B4	B5	Unplanned	Notes
Visit Description	Vax 1 Visit	1-Week Follow-Up Visit (Vax 1)	1-Month Follow-Up Visit (Vax 1)	3-Month Follow-Up Visit (Vax 1)	6-Month Follow-Up Visit (Vax 1)	Potential COVID-19 Illness Visit	The COVID-19 illness visit may be conducted as an in-person or telehealth visit. The COVID-19 illness visit is only conducted for symptomatic participants. See Section 10.8.8.5.8 .
Visit Window	Day 1	6 to 8 Days After Visit B1	28 to 35 Days After Visit B1	84 to 98 Days After Visit B1	175 to 189 Days After Visit B1	Optimally Within 3 Days After Potential COVID-19 Illness Onset	Visit B4 and Visit B5 may be performed as telehealth visits if the participant had blood draws discontinued.
Blood sample for HLA typing	~5 mL						Applicable at designated sites only. Optional with additional consent given by participants ≥18 years of age. See Section 10.8.8.2.2 .
Obtain randomization number using the IRT system	X						Refer to Section 10.8.6.4.2 .

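### The Substudy B Month 6 visit text asks for about 50 mL of blood from adults, where the schedule of activities and the stated volume totals require about 20 mL

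*Protocol*

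**What the plan says.** Three places in the protocol set or imply the adult blood volume for immunogenicity testing at Visit B5.

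- **Visit procedure, Section 10.8.8.5.5:** sites collect "approximately 50 mL for participants $\geq 18$ years of age) for immunogenicity testing, unless advised otherwise by Pfizer".
- **Schedule of activities, Section 10.8.1.3:** the row for B1 to B5 reads "50 mL/ 10 mL ~20 mL/ 10 mL ~50 mL/ 10 mL ~20 mL/ 10 mL ~20 mL/ 10 mL". The note to the row explains the two sizes: "50 mL/20 mL is to be collected from participants ≥18 years of age at time of consent", with 10 mL for those aged 12 to 17 years. The adult value at B5 is therefore about 20 mL.
- **Biological Samples, Section 10.8.8.2.4:** the stated totals are "approximately 50 mL for participants 12 through 17 years of age and approximately 160 mL for participants" aged 18 and over, rising to about 815 mL for adults who also give PBMC samples. For additional safety samples, the section requires that the total volume "does not exceed 550 mL during any period of 56 consecutive days for participants 18 years of age and older".

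The corresponding Month 6 visit in Substudy A (Section 10.7.8.5.5) uses the same sentence with the smaller volume: "approximately 20 mL for participants $\geq 18$ years of age) for immunogenicity testing, unless advised otherwise by Pfizer". Visit C6 in Substudy C (Section 10.9.8.5.6) does too.

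**The concern.** The visit text and the schedule give different volumes for the same sample at the same visit, and no rule says which one governs. A site that follows the visit text takes 2.5 times the scheduled volume and goes over the stated total. A site that follows the schedule departs from the visit text. Monitoring cannot tell from the protocol which of the two is the deviation.

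What is at stake is participant burden and consistent conduct across sites. The statistical results are not at stake. The Substudy B noninferiority comparison uses Month 1 titers, the Month 6 sample serves exploratory summaries, and either volume provides that sample.

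**Working it through.** **Inputs (adults, Substudy B)**

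| Visit | Schedule, 10.8.1.3 (mL) | Visit procedure (mL) | Procedure section |
|---|---|---|---|
| B1 | 50 | 50 | 10.8.8.5.1 |
| B2 | 20 | 20 | 10.8.8.5.2 |
| B3 | 50 | 50 | 10.8.8.5.3 |
| B4 | 20 | 20 | 10.8.8.5.4 |
| B5 | 20 | **50** | 10.8.8.5.5 |

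PBMC sampling adds 130 mL at each of the five visits, and HLA typing adds 5 mL at B1 only (Sections 10.8.1.3 and 10.8.8.2.2).

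**Step 1. Reproduce the stated totals from the schedule.**
- Without PBMC: 50 + 20 + 50 + 20 + 20 = 160 mL. Stated: about 160 mL.
- With PBMC and HLA: 160 + 5 × 130 + 5 = 815 mL. Stated: up to about 815 mL.
- Adolescents: 5 × 10 = 50 mL. Stated: about 50 mL.

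All three match exactly.

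**Step 2. Repeat with the visit procedures.**
- Without PBMC: 50 + 20 + 50 + 20 + 50 = 190 mL, which is 30 mL over. 30/160 = 18.75%.
- With PBMC and HLA: 190 + 650 + 5 = 845 mL, which is 30 mL over. 30/815 = 3.7%.
- Adolescents: 10 mL at B5 in both places, so no change.

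Neither adult total can be reached with 50 mL at B5.

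**Step 3. Check the limit of 550 mL in 56 days, taking the PBMC subset as the worst case.**
- Volume per visit: B1 = 50 + 130 + 5 = 185; B2 = 20 + 130 = 150; B3 = 50 + 130 = 180; B4 = 20 + 130 = 150; B5 = 150 with a 20 mL draw or 180 with a 50 mL draw.
- B1 to B3 fall within days 0 to 35: 185 + 150 + 180 = 515 mL.
- B3 and B4 can be as close as 84 − 35 = 49 days: 180 + 150 = 330 mL.
- B2 and B4 are at least 84 − 8 = 76 days apart, so no 56-day period contains both.
- B4 and B5 are at least 175 − 98 = 77 days apart, so B5 never shares a 56-day period with another scheduled draw and contributes at most 180 mL.

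The maximum is 515 mL with either B5 volume, below 550 mL.

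**Step 4. Compare with the parallel substudies.** Substudy A has the same five-visit volumes and the same totals of 160 mL and 815 mL (Section 10.7.8.2.4), with 20 mL at A5. In Substudy C the stated totals are also schedule sums with 20 mL at Month 6: adults in Cohort 2, 160 + 4 × 130 + 5 = 685 mL; Cohort 3, 180 + 4 × 130 + 5 = 705 mL. B5 is the only Month 6 visit that differs.

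**The case against.** The contradiction and the arithmetic are not in dispute. The case on the other side is about weight, and parts of it stand.

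- **It may no longer affect anyone.** Section 2.2.1 already reports Substudy B Month 1 results, and the protocol does not say whether any B5 visit was outstanding when Amendment 2 was issued. This stands. What can be said is that the current text carries the error. Even if every B5 visit is complete, the text still leaves unclear which volume was correct.
- **The totals are approximate and are not limits.** This also stands. The extra 30 mL exceeds a stated approximate total but breaches no cap. However, the protocol uses 20 mL and 50 mL as two distinct draw sizes, so rounding does not explain the gap.
- **The schedule should be taken to govern.** Section 10.8.8.1 makes adherence to the schedule essential. But Section 1.3 calls the schedule an overview and refers readers to the procedures section for the detail. A site has support for either reading, so this softens the conflict without resolving it.
- **The sponsor may advise a different volume.** The clause allowing this also appears in the B4 procedure, where the volume is 20 mL. It permits an override but does not set the default.
- **Not every adult is exposed.** Participants whose blood draws were discontinued may have B5 by telehealth. This is correct, and it narrows the reach a little.

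**Conclusion.** The concern holds and is minor. Section 10.8.8.5.5 is wrong as written if the schedule and the stated totals are right, and everything else in the protocol points that way: the schedule row, both adult totals, the other four visit procedures, and the Month 6 visits in the other two substudies. The size is 30 mL more per adult, once, wherever the visit text is followed. This assumes that all scheduled draws are made at their nominal volumes and within the visit windows. It does not affect adolescents, the 56-day limit, sample size, hypotheses, endpoints or analyses, and it should not be presented as a safety or analysis problem.

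**What to change.** In Section 10.8.8.5.5, change the volume for participants aged 18 years and older from about 50 mL to about 20 mL. The visit text then agrees with the schedule, the stated totals and Visits A5 and C6. If the sponsor did intend 50 mL, the alternative is to change the B5 cell in Section 10.8.1.3 and restate the totals in Section 10.8.8.2.4 as about 190 mL and 845 mL.

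The preferred change costs one number in one section and leaves design, endpoints and analysis as they are. Amendment 2 made a correction of the same kind when it aligned the Visit C3 window in the heading with the schedule, so this can go into the next amendment as a nonsubstantial change. If Month 6 samples have already been taken, the sponsor should record which volume was intended so that deviations are classified consistently.
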